12.0. DATA AND SAFETY MONITORING PLAN

The Principal Investigator will carry out ongoing trial oversight and will meet frequently with the study team to review recently acquired data and adverse events. The data recorded within the research charts and protocol database is compared with the actual data that is available from the medical record and/or clinical histories. All investigators on the protocol have received formal training in the ethical conduct of human research. The Principal Investigator will receive monitoring support as described below. Institutional support of trial monitoring will be in accordance with the FHCRC/University of Washington Cancer Consortium Institutional Data and Safety Monitoring Plan. Under the provisions of this plan, FHCRC Clinical Research Support coordinates data and compliance monitoring conducted by consultants, contract research organizations, or FHCRC employees unaffiliated with the conduct of the study. Independent monitoring visits occur at specified intervals determined by the assessed risk level of the study and the findings of previous visits per the institutional DSMP. In addition, protocols are reviewed at least annually and as needed by the Consortium Data and Safety Monitoring Committee (DSMC), FHCRC Scientific Review Committee (SRC) and the FHCRC/University of Washington Cancer Consortium Institutional Review Board (IRB). The review committees evaluate accrual, adverse events, stopping rules, and adherence to the applicable data and safety monitoring plan for studies actively enrolling or treating patients. The IRB reviews the study progress and safety information to assess continued acceptability of the risk-benefit ratio for human subjects. Approval of committees as applicable is necessary to continue the study. The trial will comply with the standard guidelines set forth by these regulatory committees and other institutional, state and federal guidelines.

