induction, starting on day 8 up to 3 days prior to the next cycle during consolidation, and then daily for 12 months after the end of consolidation. CR rates were 59% vs. 60% in the placebo vs. sorafenib arm ($p=0.76$) but median event-free survival (EFS) was 9.2 months in placebo compared with 20.5 months in sorafenib arm, translating to a 3-year EFS of 22% vs. 40% respectively ($p=0.013$). Median OS has not yet been reached and is similar in both arms. There was a higher rate of fever, bleeding, and hand-foot syndrome in the sorafenib arm. Of note, the beneficial effect of sorafenib was due mostly to results in patients who were FLT3/ITD wild-type and who comprised the majority of patients in the study, as is true in the general AML population. In contrast, Serve et al. conducted a randomized trial with sorafenib, involving 211 patients >60 years of age to either cytarabine, daunorubicin (7+3) and placebo or 7+3 in combination with sorafenib, and found higher treatment-related mortality (early death) for sorafenib vs. placebo (17% vs. 7%, $p=0.052$), and non-significantly lower CR rates in the sorafenib arm (48% vs 60%, $p=0.12$) [18]. Therefore, sorafenib given in combination with chemotherapy is not currently recommended for elderly patients with AML.

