Level -1	Mitoxantrone10 mg/m ²	Sorafenib 200 mg once daily

In addition to safety stopping rules in phase 1, we will also employ efficacy stopping rules to make sure that the regimen does not have lower response rates than our current standard. Among the first 57/61 evaluable patients treated with G-CLAM alone in our ongoing phase 1/2 study, the MRDneg CR rate was 68%. We will assume that the G-CLAM+sorafenib regimen will not be of further interest if the true MRDneg CR rate is 60% or less (null hypothesis) and that that an MRDneg CR rate of 80% or more would be of interest for further investigation (alternative hypothesis). Therefore, if MRDneg CR is seen in < 5 of the first 11 patients, consideration will be given to stopping the study. An 80% confidence interval for an MRDneg CR rate of 4/11 is 0.17-0.60. Thus the upper bound of this limit is less than the current MRDneg CR rate with G-CLAM alone (68%). However, because the first 11 G-CLAM + sorafenib patients may differ with respect to cytogenetics/age etc. from the original 57 G-CLAM patients, a decision to stop would also depend on comparative examination of patient characteristics.

14.2 Phase 2

The study will be conducted in two sequential parts. The phase 1 portion ends once an MTD is identified or dose level 6 has been completed, whichever occurs first. Patients enrolled in the Phase 1 portion and treated at the MTD dose of sorafenib and mitoxantrone will be included in the analysis of the Phase 2 portion. The primary objective of the Phase 2 portion is to evaluate the MRDneg CR rate after up to 2 courses of induction chemotherapy.

A two-stage design will be used (Simon Optimal Two-Stage). As per the phase 1 section above, the MRDneg CR rate of our historical control of G-CLAM alone is 68%. G-CLAM+sorafenib will not be of further interest if the true MRDneg CR rate is 60% or less (null hypothesis) and that that an MRDneg CR rate of 80% or more would be of considerable interest for further investigation (alternative hypothesis). Therefore, in the first stage, 19 eligible patients will be accrued. If necessary, the study may be temporarily closed while remission data is collected. If at least 12 of the first 19 patients achieved an MRDneg CR (63%), we will move to the second stage. The second stage would enroll another 22 patients (for a total of 41), with G-CLAM + sorafenib considered of interest (at least 80% MRDneg CR rate) if at least 31/41 attained

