APPENDIX A: TREATMENT-RELATED MORTALITY (TRM) SCORE

Calculation of Simplified Treatment-Related Mortality (TRM) Score

Includes covariates: performance status (PS), age, platelet count, albumin, secondary AML, white blood cell count (WBC), peripheral blood blast percentage, and creatinine

Score = $100/(1+e^{(-x)})$, with $x = -4.08 + 0.89*PS + 0.03*age - 0.008*platelet count - 0.48*albumin + 0.47*(have secondary AML) + 0.007*WBC - 0.007*(peripheral blood blast percentage) + 0.34*creatinine$

Probability of TRM Above and Below Various Simplified TRM Score Cut-offs

TRM Score Interval	Patients below/within/above TRM Score Interval (%)	TRM Probability if below TRM Score Interval (%)	TRM Probability if within TRM Score Interval (%)	TRM Probability if above TRM Score Interval (%)
0 – 1.9	0/20/80	-	1	12
1.91 – 3.9	20/20/60	1	2	16
3.91 – 6.9	40/20/40	1	7	20
6.91 – 9.2	60/10/30	3	7	24
9.21 – 13.1	70/10/20	4	12	31
13.11 – 22.8	80/10/10	5	20	41
22.81 – 100	90/10/0	6	41	-

From: Walter RB, Othus M, Borthakur G, Ravandi F, Cortes JE, Pierce SA, Appelbaum FR, Kantarjian HM, Estey EH. Prediction of early death after induction therapy for newly diagnosed acute myeloid leukemia with pretreatment risk scores: a novel paradigm for treatment assignment. *J Clin Oncol*. 2011;29(33):4417-4424.

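### Phase 2 has no early-death or toxicity boundary; its one interim rule, the response look at 19 patients, picks up excess deaths only indirectly and weakly

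*Combined protocol and SAP*

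**What the plan says.** - **Oversight (12.0).** The Principal Investigator meets the study team frequently. The monitoring committee, scientific review committee and IRB review the protocol at least once a year and otherwise as needed. Of these bodies the section says: "The review committees evaluate accrual, adverse events, stopping rules", among other things.
- **Phase 1 (8.3, 14.1).** DLTs in Cycle 1 steer dose escalation in cohorts of 6, expandable to 12. The efficacy check on the first 11 patients is introduced with "In addition to safety stopping rules in phase 1". Before phase 2 opens, all grade 3 or higher events from phase 1 are reviewed, and doses may be reduced.
- **Phase 2 (14.2).** "If at least 12 of the first 19 patients achieved an MRDneg CR (63%), we will move to the second stage". The regimen is then of interest "if at least 31/41 attained" MRD-negative CR. Phase 1 patients treated at the chosen doses count toward the first 19. No limit on deaths or toxicity is given.
- **Termination (15.0).** This section refers the reader to section 15.0, that is, to itself. It lets the Principal Investigator, IRB or FDA end the study at any time.
- **Background (1.0).** A randomized trial of 211 patients over 60, on 7+3 with or without sorafenib, found "higher treatment-related mortality (early death) for sorafenib vs. placebo": 17% against 7%, p=0.052.
- **Expected mortality (3.1.4, Appendix A).** Eligibility requires a TRM score of 13.1 or less. The table headed "Probability of TRM Above and Below Various Simplified TRM Score Cut-offs" gives 5% TRM for patients below the 13.11–22.8 interval.

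**The concern.** The combination is new: section 1.0 says that sorafenib has not been added to G-CLAM before, and mitoxantrone is escalated at the same time. Phase 1 judges each level on 6 to 12 patients, too few to exclude a material rise in early death. Phase 2 is where such a rise would become visible, but the plan names no number of deaths that should prompt a review. The committees are told to assess stopping rules, and the only phase 2 rule they can find concerns response. At stake is how many patients are treated before someone is obliged to look.

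**Working it through.** **1. The plan's own figures.** The trial stops at stage 1 if 11 or fewer of 19 respond. At a true rate of 60%, P(X ≤ 11 | n=19) = 51.2% (plan: 51%). Mean enrolment is 19 + 22 × (1 − 0.512) = 29.7 (plan: 29). The look is therefore read correctly here.

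**2. Patients without a numeric safety rule.** Of the 41, 6 to 12 may be phase 1 patients at the phase 2 dose: 41 − 12 = 29 and 41 − 6 = 35.

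**3. What phase 1 can exclude.** Suppose early death is 17% and every such death counts as a DLT. A cohort of 6 has 0 or 1 with probability 0.83⁶ + 6 × 0.17 × 0.83⁵ = 73%, and escalation continues. A cohort of 12 has 3 or fewer with probability 87%. Section 8.3.2 also exempts infection unless it is felt to be a direct consequence of treatment toxicity, so whether a septic death counts is a judgement.

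**4. Expected deaths in 41.** At 5%: 41 × 0.05 = 2.1. At 17%: 41 × 0.17 = 7.0.

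**5. What the look at 19 does with excess deaths.** Deaths among evaluable patients are non-responses. Assume a response rate R when early death is 7%, and no change in response among survivors. Survivor response is q = R/0.93, and overall response at 17% early death is 0.83q.

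| R at 7% death | q | Overall at 17% death | Stop at 19, before | Stop at 19, after |
|---|---|---|---|---|
| 80% (design alternative) | 0.860 | 71.4% | 2.3% | 14.7% |
| 68.4% (historical G-CLAM) | 0.735 | 61.0% | 22.6% | 47.4% |

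Up to 19 − 12 = 7 deaths in 19 are compatible with continuing if every other patient responds. Section 14.2 replaces patients who received less than 75% of Cycle 1 chemotherapy and states no exception for death. In the extreme case where every early death is replaced, the stop probabilities fall to P(X ≤ 11 | 19, q) = 0.3% and 10%.

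**6. An illustrative boundary.** Pause at 3 or more deaths in 10, 4 or more in 19, or 5 or more in 30. Exact sequential binomial probability of triggering:

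| True early death | 5% | 7% | 10% | 17% | 20% |
|---|---|---|---|---|---|
| P(trigger) | 2.8% | 8.0% | 21.6% | 63.3% | 77.2% |

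**7. Mean enrolment at 17% early death.** The current plan gives 19 + 22 × (1 − stop probability). The second figure applies the boundary and the response look together, with a pause treated as a stop.

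| Case | Current plan | With boundary |
|---|---|---|
| R = 80% | 37.8 | 26.8 |
| R = 68.4% | 30.6 | 24.1 |
| 76% response among survivors (0.83 × 0.76 = 63.1% overall; stop probability 40%) | 32.2 | 24.9 |

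The saving is about 6 to 11 patients.

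**The case against.** **The look at 19 is a safeguard of sorts.** A reader might infer that excess mortality could run to 41 patients with no rule able to stop it. The documents do not support that: evaluable patients who die are non-responders and can fail the 12/19 test. For the same reason, a fall in mean enrolment from 41 to about 27 (the boundary alone at 17%) would overstate the gain, because 41 ignores the futility stop already in the plan. This stands, and step 7 allows for it.

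**The 17% comes from another population.** That trial treated patients over 60 on 7+3, with p=0.052, and the protocol uses it to advise against the combination in elderly patients. This trial enrols ages 18 to 60. Closer to its population, section 1.0 reports that sorafenib up to 400 mg twice daily was well tolerated with idarubicin and cytarabine in patients under 65, and that survival was similar in both arms of the younger-adult randomized trial. This also stands: 17% is a stress scenario and not a forecast.

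**Other oversight exists.** There is the grade 3 or higher review before phase 2, as-needed committee review, and power to terminate at any time. Related, serious and unexpected events go to the IRB within ten days, and under 11.2.4 an unusual frequency can make an event unexpected. These safeguards are real, but none states a number of deaths that triggers action. Section 11.2.5 also leaves simple complications of myelosuppression, including infection and bleeding, to the annual report, without saying when a fatal infection ceases to be one. The institutional monitoring plan cited in 12.0 is not among the documents and might hold a trigger; if so, 14.2 should cite it.

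**Conclusion.** The concern holds in a limited form. Phase 2 has no early-death or toxicity boundary, its single interim look is a weak proxy for one, and nothing numeric applies between patients 20 and 41. The documents do not show that excess mortality would go unchecked to 41, nor that 17% is to be expected here.

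The 15% to 47% stop probability assumes 7% early death as the starting point, unchanged response among survivors, and deaths counted as failures. The 5% reference is a pooled figure from Appendix A for scores below the cut, not an early-death rate observed with this regimen. The enrolment saving further assumes that a pause becomes a stop. The absence of a boundary depends on none of these assumptions. It is a gap that should be closed, not an error that invalidates the design.

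**What to change.** Add to 14.2 an early-death boundary for patients treated at the phase 2 dose. Crossing it pauses accrual for review by the monitoring committee; it does not close the trial automatically. The text should:

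- fix the death window in advance;
- count all treated patients, including phase 1 patients at that dose and anyone replaced as non-evaluable;
- give the limits and a table of operating characteristics such as the one in step 6;
- be cross-referenced from 12.0 and 15.0, with the self-reference in 15.0 corrected.

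The limits of 3/10, 4/19 and 5/30 are an example, and the sponsor may choose others. A tighter set of 2/10, 3/19 and 4/30 triggers with probability 83% at a true 17%, but 13% at 5%.

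The cost is a paragraph and a small table. With the example limits, the chance of an unnecessary pause is about 3% if true early death is 5%, and 8% if it is 7%.

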13.0 ETHICAL AND REGULATORY CONSIDERATIONS

13.1 Institutional Review Board

In accordance with federal regulations (21 CFR 312.66), an Institutional Review Board (IRB) that complies with regulations in 21 CFR 56 must review and approve this protocol and the informed consent form prior to initiation of the study.

13.2 Consent

The Principal Investigator or her designee must explain verbally and in writing the nature, duration, and purpose of the study and possible consequences of treatment. Patients must also be informed that they may withdraw from the study at any time and for any reason without jeopardizing their future treatment. In accordance with federal regulations (21 CFR 50), all patients enrolled in the study must sign the IRB-approved consent form.

13.3 Confidentiality

Patient medical information obtained for the purposes of this study is confidential, and disclosure to third parties, other than those noted below, is prohibited. Upon the patient's request and written permission, medical information may be given to his/her personal physician or other appropriate medical personnel responsible for the patient's welfare. Data generated for this study

must be available for inspection on request to representatives of the national or local health authorities, and the associated IRB/IEC. Release of research results or data that reveal patient names or other identifiers, such as photographs, audio or videotapes, must be carried out in accordance with Department of Health and Human Services Final Standards for Privacy of Individual Health Information, 45 CFR 164.508. Written authorization must be obtained from the patient and IRB/IEC prior to the release of such information. Identifiable patient data may not be used for purposes of promoting any drugs used in this trial.

13.4 Publication Statement

The results of this clinical trial may be used for public dissemination in the form of papers, abstracts, posters, or other informational materials to be presented at scientific meetings, or published in professional journals, or as a part of an academic thesis by an investigator. Identifiable patient data may not be used for any of these presentations, manuscripts, or reports unless directed by law.

14.0 STATISTICAL CONSIDERATIONS

14.1 Phase 1

14.1.1 General Considerations: DLTs are defined in Section 8.3. DLTs occurring during Cycle 1 will be used to guide dose escalation. However, before the phase 2 portion is begun, all grade ≥ 3 adverse events of all patients treated in the phase 1 portion will be reviewed to assess for late and cumulative toxicities that were not captured during the phase 1 portion of the trial. The Principal Investigator reserves the right to modify the protocol to reduce the drug doses identified in the phase 1 portion if this assessment suggests a significant risk of late/cumulative toxicities. Patients will be considered evaluable for DLT if they received at least 75% of the assigned doses of each chemotherapeutic during Cycle 1 or if they developed a DLT. If a patient does not develop a DLT but does not receive at least 75% of treatment during Cycle 1, the patient will be considered not evaluable for DLT and will be replaced. Maximum tolerated dose (MTD) is defined as the highest dose studied in which the incidence of DLT is $<33\%$ assuming at least 6 patients have been treated at this dose.

14.1.2 Dose Escalation scheme:

Starting with dose level K=1:

A. Evaluate 6 patients at dose level K

- a. If 0 or 1 have DLT, increase dose to K+1 and go to A
- b. If 2 have DLT, stop dose escalation
- c. If >2 have a DLT, go to dose K-1

The dose level below that which dose escalation was stopped is the potential MTD.

In order to better define safety and initial evidence of anti-leukemia activity while waiting for patients to complete their treatment cycles to assess the MTD, any dose level cohort may be expanded up to 12 patients, provided that

2 or fewer of 6 patients had DLT at that dose level (ie at least 4/6 have had no DLT). the cohort is expanded to 7-11 patients, these patients will not count toward DLT and MTD evaluation. If a cohort is expanded to 12 patients, the following rules will determine further dose escalation:

If 3 or fewer have DLT, increase dose to K+1 (go to A)

If 4 or more have DLT, stop dose escalation

Dose-finding for both mitoxantrone and sorafenib:

Level 1	Mitoxantrone10 mg/m ²	Sorafenib 200 mg BID
Level 2	Mitoxantrone12 mg/m ²	Sorafenib 200 mg BID
Level 3	Mitoxantrone15 mg/m ²	Sorafenib 200 mg BID
Level 4	Mitoxantrone18 mg/m ²	Sorafenib 200 mg BID
Level 5	Mitoxantrone18 mg/m ²	Sorafenib 400mg AM, 200 mg PM
Level 6	Mitoxantrone18 mg/m ²	Sorafenib 400 mg BID
Level -1	Mitoxantrone10 mg/m ²	Sorafenib 200 mg once daily

In addition to safety stopping rules in phase 1, we will also employ efficacy stopping rules to make sure that the regimen does not have lower response rates than our current standard. Among the first 57/61 evaluable patients treated with G-CLAM alone in our ongoing phase 1/2 study, the MRDneg CR rate was 68%. We will assume that the G-CLAM+sorafenib regimen will not be of further interest if the true MRDneg CR rate is 60% or less (null hypothesis) and that that an MRDneg CR rate of 80% or more would be of interest for further investigation (alternative hypothesis). Therefore, if MRDneg CR is seen in < 5 of the first 11 patients, consideration will be given to stopping the study. An 80% confidence interval for an MRDneg CR rate of 4/11 is 0.17-0.60. Thus the upper bound of this limit is less than the current MRDneg CR rate with G-CLAM alone (68%). However, because the first 11 G-CLAM + sorafenib patients may differ with respect to cytogenetics/age etc. from the original 57 G-CLAM patients, a decision to stop would also depend on comparative examination of patient characteristics.

14.2 Phase 2

The study will be conducted in two sequential parts. The phase 1 portion ends once an MTD is identified or dose level 6 has been completed, whichever occurs first. Patients enrolled in the Phase 1 portion and treated at the MTD dose of sorafenib and mitoxantrone will be included in the analysis of the Phase 2 portion. The primary objective of the Phase 2 portion is to evaluate the MRDneg CR rate after up to 2 courses of induction chemotherapy.

A two-stage design will be used (Simon Optimal Two-Stage). As per the phase 1 section above, the MRDneg CR rate of our historical control of G-CLAM alone is 68%. G-CLAM+sorafenib will not be of further interest if the true MRDneg CR rate is 60% or less (null hypothesis) and that that an MRDneg CR rate of 80% or more would be of considerable interest for further investigation (alternative hypothesis). Therefore, in the first stage, 19 eligible patients will be accrued. If necessary, the study may be temporarily closed while remission data is collected. If at least 12 of the first 19 patients achieved an MRDneg CR (63%), we will move to the second stage. The second stage would enroll another 22 patients (for a total of 41), with G-CLAM + sorafenib considered of interest (at least 80% MRDneg CR rate) if at least 31/41 attained

MRDneg CR. The probability of declaring a therapy of interest when it is not is 10% (type-1 error), and not of interest when it is, is 20% (power 80%). Under the null hypothesis (true MRDneg CR rate 60%) the probability of termination before enrolling 41 patients is 51% and the average sample size is 29 patients. Note that patients treated at the recommended sorafenib and mitoxantrone doses during the Phase 1 part of the study would count toward the first 19 patients. Patients will be considered not evaluable if they received less than 75% of the assigned doses of each chemotherapeutic agent during Cycle 1, and they will be replaced. If a patient does not receive at least 75% of their assigned dose of sorafenib but discontinues the drug due to toxicity, they will be considered evaluable as we want to capture this essential toxicity data (and its potential downstream effect on efficacy) and not be replaced.

QOL scores, resource utilization, and cost variables will be recorded and summarized using descriptive methods including boxplots, histograms, and statistical summary measures (medians, means, standard deviation, N, and proportions). This study will not be powered to detect statistically significant differences between these endpoints for those with different responses; rather we will record these outcomes to inform a subsequent larger study, should follow up investigations be warranted.

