- 6.3.1 For induction: patients will receive sorafenib and mitoxantrone at 1 of 6 total dose levels as allocated (see section Dose Escalation Scheme page 2 or 15.1.2). Mitoxantrone will be given IV daily over 60 minutes Days 1-3 and sorafenib orally Days 10-19 for all levels. Allowances of +/- 2 days for this window will be allowed for logistical purposes. Levels are as follows: Level 1, mitoxantrone 10 mg/m² with sorafenib 200 mg PO twice daily; Level 2, mitoxantrone 12 mg/m² with sorafenib 200 mg PO twice daily; Level 3, mitoxantrone 15 mg/m² with

sorafenib 200 mg PO twice daily; Level 4, mitoxantrone 18 mg/m² with sorafenib 200 mg PO twice daily; Level 5, mitoxantrone 18 mg/m² with sorafenib 400 mg PO in the morning and 200 mg in the evening; Level 6, mitoxantrone 18 mg/m² with sorafenib 400 mg PO twice daily. Level -1, dosed at mitoxantrone 10 mg/m² and sorafenib 200 mg PO once daily will also be available for dose de-escalation due to toxicities, as described in Section 6.8. For baseline organ dysfunction within the allowable limits of the eligibility criteria, dose reduction of individual medications specific to the organ impairment (e.g. liver, kidney) are allowed but not required, as described in section 6.10, and should be done in conjunction with the Oncology Pharmacist and PI.

- 6.3.2 The dose of mitoxantrone is calculated using the patient's actual weight.
- 6.3.3 For post-remission therapy: sorafenib will be given per dose level as above, starting on day 8 until day 27 or 3 days prior to next cycle of treatment, whichever occurs first. Allowances of +/- 3 days for this window will be allowed for logistical purposes (i.e. timing of clinic visit for count evaluation).
- 6.3.4 For maintenance: sorafenib will be given daily for up to 12 months following post-remission at the final dose the patient received during induction, with subsequent dose adjustment based on blood counts and extra-medullary toxicities.
- 6.3.5 All treatment is given as intent-to-treat; missed doses will not be made up.

6.4 **Administration of G-CSF, Cladribine, and Cytarabine**

- 6.4.1 The doses of the elements of G-CLAM chemotherapy will be as follows: G-CSF 5 µcg/kg rounded to 300 or 480 µcg daily subcutaneously daily on Days 0-5, Cladribine 5 mg/m² IV daily over 2 hours on Days 1-5, and Cytarabine 2 g/m² IV daily over 2 hours on Days 1-5.
- 6.4.2 The doses of G-CSF, cladribine, and cytarabine are calculated using the patient's actual weight.

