8.3 Definition of Dose-limiting Toxicities (DLTs)

Reported adverse events and potential risks for G-CSF, cladribine, cytarabine, and mitoxantrone, are described in section 7. Dose-limiting toxicities (DLTs) used to guide dose escalation in this trial are defined as follows:

- 8.3.1** Any Grade ≥ 3 non-hematologic toxicity lasting >48 hours that results in >7 day delay of the subsequent treatment cycle, with the exception of febrile neutropenia or infection.
- 8.3.2** Any Grade ≥ 4 non-hematologic toxicity with the exception of febrile neutropenia/infection unless felt to be a direct consequence of treatment-related toxicity (e.g. intestinal infection following mucosal barrier breakdown), and with the exception of constitutional symptoms if no recovery to Grade ≤ 2 within 14 days.
- 8.3.3** Hematologic toxicity with ANC $<500/\mu\text{L}$ or platelet count $<50,000/\mu\text{L}$ for >49 days after initiation of G-CLAM, in conjunction with bone marrow showing no evidence of MRD or persistent AML.

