Grade ≥ 3 adverse events other than hematologic toxicities will be recorded, graded, and reported as appropriate. AEs will be collected from the time of consent until 60 days after day 1 of each cycle or until the patient receives an alternative anti-cancer therapy, whichever date comes first. AEs that do not meet the requirement for expedited reporting will be reported to the IRB as part of the annual renewal of the protocol.

Myelosuppression and associated complications are expected events during leukemia therapy; therefore, myelosuppression and associated simple complications such as fever,

infections, bleeding, and related hospitalizations will not be reported as individual AE but will be summarized in the annual report to the IRB.

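### DLT evaluability in Section 14.1.1 rests on doses received alone, so a fully dosed patient who leaves before the DLT criteria can be judged counts as DLT-free

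*Combined protocol and SAP*

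**What the plan says.** Section 14.1.1 ties escalation to the first cycle: "DLTs occurring during Cycle 1 will be used to guide dose escalation". It gives that cycle no length in days. Evaluability is a dose condition: "Patients will be considered evaluable for DLT if they received at least 75% of the assigned doses of each chemotherapeutic during Cycle 1", or the occurrence of a DLT. The replacement rule covers one case only: "If a patient does not develop a DLT but does not receive at least 75% of treatment during Cycle 1". Under 14.1.2, 0 or 1 DLT in six patients escalates and 2 stops escalation. In a cohort expanded to 12, 3 or fewer escalates and 4 or more stops.

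The DLT definitions in Section 8.3 need more time than dosing does:
- 8.3.1 requires that a Grade 3 or higher non-hematologic toxicity delay the next cycle by more than 7 days.
- 8.3.2 covers Grade 4 or higher non-hematologic toxicity, with a 14-day recovery element for constitutional symptoms.
- 8.3.3 requires ANC below 500/µL or platelets below 50,000/µL "for >49 days after initiation of G-CLAM", with a marrow free of MRD and AML.

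Section 6.14 lists other leukemia therapy and consent withdrawal among the reasons for removal. Under 11.2.5, non-hematologic Grade 3 or higher AEs are collected to 60 days after day 1 of each cycle, or "until the patient receives an alternative anti-cancer therapy, whichever date comes first".

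**The concern.** Receiving the dose and being observed for its toxicity are different things, and the rule asks only for the first. A patient who has had the required doses, has shown no DLT so far and then leaves is evaluable, has no DLT on record and is not replaced. That patient stays in the denominator as a safe outcome, although one or more DLT criteria could not yet have been judged.

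In cohorts of six, a single unseen event can turn a stop into an escalation. An unseen DLT can only lower the count, so the error runs one way: towards escalation and a higher MTD. The MTD then sets the phase 2 dose, and phase 1 patients treated at it enter the phase 2 analysis (Section 14.2).

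**Working it through.** **1. The plan's own figure.** Section 14.1.1 puts the MTD limit at a DLT incidence below 33%. The cut-offs agree with it: 1/6 = 16.7% and 3/12 = 25.0% escalate; 2/6 = 4/12 = 33.3% stop. The plan gives no operating characteristics for the rule.

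**2. When the dose condition is met.** Inputs from Section 6: "Mitoxantrone will be given IV daily over 60 minutes Days 1-3 and sorafenib orally Days 10-19 for all levels"; "Cladribine 5 mg/m² IV daily over 2 hours on Days 1-5, and Cytarabine 2 g/m² IV daily over 2 hours on Days 1-5".
- Cladribine and cytarabine: 4 of 5 doses = 80% (3 of 5 = 60% is too few), so Day 4.
- Mitoxantrone: 2 of 3 = 67% is too few, so 3 of 3, Day 3.
- G-CSF, Days 0-5: 5 of 6 = 83%, Day 4.
- Sorafenib twice daily: 0.75 × 20 = 15 doses; 15/2 = 7.5 days, so the eighth dosing day, Day 17. Section 6.3.1 adds: "Allowances of +/- 2 days for this window will be allowed for logistical purposes". That gives about Days 15-19.

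The condition is thus met about Day 17 if sorafenib is a chemotherapeutic, and about Day 4 if not. Section 6.10 deals with sorafenib under chemotherapeutic drugs, which supports Day 17.

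**3. Gap to the hematologic criterion.** From Day 17: 49 − 17 = 32 days. From Day 4: 49 − 4 = 45 days. A patient who leaves later loses less: departure on Day 20 leaves 29 days and on Day 35 leaves 14.

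**4. Who can be missed.**
- *8.3.3:* only a patient with unrecovered counts and no AML or MRD who leaves before Day 49. Recovered counts, or a marrow with AML or MRD, rule the criterion out.
- *8.3.3 and a second course:* the Study Overview in Section 6.0 holds the next course in an aplastic marrow, but defines non-recovery as ANC below 500 *and* platelets below 50,000. Section 8.3.3 (like 6.14.5) uses *or*. A patient low in only one lineage may fall outside the hold, and 6.6.3 allows a second course in CRi/CRp whatever the MRD status.
- *8.3.1 and 8.3.2:* patients who leave before the toxicity, or the delay of a next cycle, can be seen.

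**5. Effect on escalation.** With six fully observed patients, P(escalate) = (1 − p)^6 + 6p(1 − p)^5. Suppose m patients leave and a share L of their DLTs would come after departure. Each leaver then has a seen-DLT probability of p(1 − L).

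Upper bound, L = 1, p = 1/3:
- m = 0: 64/729 + 192/729 = 256/729 = 0.351
- m = 1 (five patients can show a DLT): 32/243 + 80/243 = 112/243 = 0.461
- m = 2 (four patients): 16/81 + 32/81 = 48/81 = 0.593

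Half late, L = 0.5, p = 0.33, m = 1 (leaver probability 0.165): 0.67^5 × 0.835 + 5 × 0.33 × 0.67^4 × 0.835 + 0.67^5 × 0.165 = 0.113 + 0.278 + 0.022 = 0.413.

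| True rate | Late share L | m = 0 | m = 1 | m = 2 |
|---|---|---|---|---|
| 1/3 | 100% (upper bound) | 0.351 | 0.461 | 0.593 |
| 0.33 | 50% | 0.358 | 0.413 | 0.473 |
| 0.33 | 25% | 0.358 | 0.385 | 0.414 |
| 0.40 | 100% (upper bound) | 0.233 | 0.337 | 0.475 |
| 0.40 | 50% | 0.233 | 0.285 | 0.346 |

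The starting values of 35% and 36% differ only because 1/3 is not exactly 0.33. The documents give neither m nor L.

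**The case against.** The case for leaving the rule alone is that few patients are affected and that other text limits the damage. Much of this stands.

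- *AE recording.* A reader might infer that AE recording stops for anyone who leaves. It does not. Section 11.2.5 keeps it open to Day 60, past Day 49, for a patient who merely stops protocol treatment. It ends early on a switch to other anti-cancer therapy and, in effect, on consent withdrawal. Hematologic toxicity is outside AE recording altogether, so for 8.3.3 the loss is of count and marrow follow-up.
- *Second course.* A reader might infer that any CRi/CRp patient re-treated at about Day 35 escapes 8.3.3. The hold in the Study Overview prevents most of this: release by count recovery means the 8.3.3 thresholds have been cleared, and release by blasts of 5% or more means AML is present. Only the single-lineage mismatch remains.
- *Leaving at any time.* Section 6.14.8 says this of consent withdrawal only. Section 6.14.3 makes other therapy a reason for removal, and 6.4.6 bars such therapy on protocol.
- *Early observation.* A leaver has been watched through chemotherapy and up to departure, so some DLTs would already have been seen.
- *Safeguards.* Section 14.1.2 speaks of waiting for patients to complete their cycles. Section 14.1.1 requires a review of all Grade 3 or higher AEs before phase 2, with authority to reduce doses.

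The safeguards do not answer the point. Neither changes who is in the DLT denominator. The review draws on AE records that stop at a switch and omit hematologic toxicity.

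**Conclusion.** The point holds in this limited form. Section 14.1.1 sets no observation requirement and no other section supplies one, so the rule as written scores a fully dosed early leaver as DLT-free. That classification follows from the rule; the protocol does not state it in words.

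The increases from 35% to 46% and 59% are upper bounds, not expected effects, because they assume that no DLT of a leaver is ever seen. With half of leavers' DLTs late, the rise at a 33% rate is from 36% to about 41% and 47%. With no early leavers there is no effect. All of these rest on assumed leaver numbers (one or two of six) and, below the upper bound, an assumed late share. Nor is 32 days a minimum unobserved period: it applies to departure on Day 17, with sorafenib counted.

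The documents do not show that any cohort was misjudged. They do show a rule whose only possible error is towards escalation and which is cheap to close.

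**What to change.** In Section 14.1.1, define a DLT-free evaluable patient as one who received at least 75% of Cycle 1 doses *and* was observed until each criterion in 8.3 can be judged:
- *8.3.3:* count recovery above its thresholds, documented AML or MRD, or passing Day 49.
- *8.3.1:* start of the next cycle, or a documented toxicity status showing whether the delay criterion is met.
- *8.3.2:* observation long enough to see the toxicity and, where it applies, to complete the 14-day recovery assessment.

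State also whether sorafenib counts as a chemotherapeutic for the 75% condition.

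Patients who leave earlier without a DLT, for reasons unrelated to toxicity, are not evaluable and are replaced. Those who leave because of toxicity are not replaced and are reviewed against 8.3.

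In the AE collection text of 11.2.5, add that in phase 1, Grade 3 or higher AEs and blood counts continue to be recorded through the Cycle 1 DLT window after a switch of therapy, unless consent is withdrawn. Reconcile the *and* in the Study Overview of Section 6.0 with the *or* in 8.3.3.

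If phase 1 has already closed, apply the definition as a check that each patient scored DLT-free was actually observed.

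The cost is protocol wording, an occasional replacement and a short wait in slow-recovering patients. The blood counts are already suggested monitoring under 6.5.1.
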